- **4.8 Confidentiality.** Participants will be required to sign a Subject Information and Consent form. All information collected for this study will be coded and remain confidential to the extent provided by law. The principal investigator will routinely review the methods of data collection and storage to ensure that no breach of confidentiality occurs. If the results of this study are submitted for publication, confidentiality of records will be maintained. Research records will be kept for a period of at least 5 years after the study ends.
- **4.9 Alternative Treatments.** Not Applicable.
- **4.10 New Information.** Participants will be promptly notified if any new information, either good or bad, develops during the course of this study that may cause a change of mind about continuing to participate.
- **4.11 Costs and Payments.** There are no costs for participating in this study. Participants receive payment for completion of each portion of the study in which they participate (see table below).

| Drot | toco | 1 | ٠. |
|------|------|---|----|
| 10 | | | ٠. |

| •• | | | |
|-------|------------|---------|--|
| Phase | # subjects | Payment | |

| Baseline | 420 | \$100* |
|-----------------------|-----|--------|
| Follow-Up (6 months) | 280 | \$75 |
| Follow-Up (12 months) | 420 | \$75 |
| Follow-Up (24 months) | 140 | \$75 |

^{* \$50} if a valid neuropsychological assessment is available allowing the protocol to be shortened

Protocol 2:

| Phase | # subjects | Payment | |
|----------|------------|---------|--|
| Baseline | 400 | \$100* | |

^{* \$50} if a valid neuropsychological assessment is available allowing the protocol to be shortened

Protocol 3:

| Phase | # subjects | Payment |
|-------------------|------------|---------|
| Report Validation | 60 | \$100 |

4.12 Conflict of Interest. The Principal Investigator, [name], is employed by Psychology Software Tools (PST) and may be perceived to be affected by the outcome of the research study. Therefore, each Subject Information and Consent form discloses this relationship where it is stated "PST employs [name], the principal investigator, who might benefit from commercial use of this product."

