Change in test scores will be modelled using a Reliable Change Index (RCI) method to determine whether the change in test scores is due to the reliability of the measure (rather than due to chance alone). This method is beneficial because it is well-documented and is one that accounts for measurement error and practice effect (Chelune et al., 1993; Hensel, 2007). It has also been shown (Hsu et al., 1999) to account for regression to the mean. Reliable change will be evaluated at the 6-month, one-year, and two-year intervals.

Using normative data from a prior sample, and data gathered from the non-impaired clinical group, an appropriate strategy will be identified for the identification of cut-off scores for clinically significant change (Jacobson and Truax, 1991). Data will then be used to derive standard error of the mean (SEm), test-retest reliability coefficients, and standard error of the difference (SEdiff) statistics. The latter, SEdiff, will identify the variability in the distribution of the change scores that would be expected if there were no change between test and retest. Finally, 90% and 95% confidence intervals will be calculated to identify the amount of difference that would have to be observed in either direction to assume that the difference occurred beyond chance (at significance levels of 5% and 2.5%, respectively).

Reliable change will be calculated using the following formula for all data regardless of clinical group:

$$RC = \frac{x_2 - x_1}{SE_{diff}}$$

Using established methods (Chelune et al. 1993), index scores will classify patterns of change as "gain", "no change", and "loss". Likewise, the same individuals will be grouped based on change in clinical adjudication between those identified as impaired, intermediate, and non-impaired at each assessment, categorizing status change as "improved", "no change", and "declined". These groups will be analyzed based on the confidence intervals, accuracy, and reliable change index. Analysis will include the assessment of practice effect.

References

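### Does calling SEm the standard error of the mean, with no formula for SEdiff, undermine the reliable change index?

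*SAP*

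**What the plan says.** The Change Metric section of the SAP adopts a reliable change index and says of the method that it "is one that accounts for measurement error and practice effect". After describing the data sources (a prior normative sample and the non-impaired group), it continues: "Data will then be used to derive standard error of the mean (SEm), test-retest reliability coefficients, and standard error of the difference (SEdiff) statistics". The next sentence explains that SEdiff "will identify the variability in the distribution of the change scores that would be expected if there were no change between test and retest".

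It then says that "90% and 95% confidence intervals will be calculated to identify the amount of difference that would have to be observed in either direction", and attaches rates to these intervals: "at significance levels of 5% and 2.5%, respectively". Finally: "Reliable change will be calculated using the following formula for all data regardless of clinical group". The formula is RC = (x2 - x1)/SEdiff, and the result classifies each person as gain, no change or loss.

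Neither the SAP nor the protocol gives a formula for SEm or SEdiff, a reliability coefficient, or the size of the reference group.

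**The concern.** The standard error of the mean has no place in a rule for judging one person's change. It measures how precisely a group average is known, so it falls as more people are tested and takes no account of how repeatable the test is. A reliable change index needs the standard error of measurement, which depends on the test-retest reliability r and not on n. The SAP names the first where the second belongs, and no formula shows which is used.

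SEdiff is the only denominator of RC, and RC is applied to everyone. If the wrong quantity fed into SEdiff, the limits would be far too narrow and most stable people would be labelled as changed. The limits could also differ between visits merely because attendance differs. Protocol section 4.11 plans 280 people at 6 months, 420 at 12 months and, at the last visit, "Follow-Up (24 months) | 140".

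Separately, the 5% and 2.5% levels follow wording about change in either direction with no per-direction label. A reader might take them as total false-change rates.

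**Working it through.** **The stated levels.** The inputs are the 90% and 95% intervals in the SAP's Change Metric section. Per-direction rate = (1 - confidence level)/2.

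- 90%: (1 - 0.90)/2 = 0.05, z = 1.645.
- 95%: (1 - 0.95)/2 = 0.025, z = 1.960.

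Both match the SAP exactly. Read as two-sided totals, 5% and 2.5% would belong to 95% and 97.5% intervals (z = 1.960 and 2.241), which are not the intervals stated. Only the per-direction reading fits, and the totals follow as 10% and 5%.

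**What the feared error would do.** This needs a formula that the SAP does not contain, SEdiff = sqrt(2)*SEm, and assumed values of r and n.

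- With the standard error of measurement: SEdiff = SD*sqrt(2(1-r)).
- With the standard error of the mean: SEdiff = SD*sqrt(2/n).
- Ratio of the first to the second: sqrt(n(1-r)).
- Share of stable people outside the 90% limits under the second: 2*(1 - Phi(1.645/sqrt(n(1-r)))).

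| Assumed n | Assumed r | Ratio | Flagged at 90% (target 10%) |
|---|---|---|---|
| 50 | 0.9 | 2.2 | 46% |
| 100 | 0.8 | 4.5 | 71% |
| 280 | 0.8 | 7.5 | 83% |
| 280 | 0.7 | 9.2 | 86% |

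On the same assumption, the limits at 12 and 6 months would be sqrt(140/420) = 0.58 and sqrt(140/280) = 0.71 times those at 24 months. That also requires n to follow attendance. The section 4.11 counts cover all clinical groups, whereas the cut-off strategy draws on the non-impaired group and a prior sample of unstated size.

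**What the text leads to.** The SAP lists SEm, the reliability coefficients and SEdiff side by side. It does not say that SEdiff is computed from SEm. It does say what SEdiff is: the spread of individual change scores under no true change. For equal SDs at test and retest, the variance of x2 - x1 is SD^2 + SD^2 - 2*r*SD^2 = 2*SD^2*(1-r), so its standard deviation is SD*sqrt(2(1-r)). That is the correct denominator, obtained from the SAP's own definition without using SEm. It contains no n. At an assumed r = 0.8 it is 0.63 SD, and the 90% limit is 1.645*0.632 = 1.04 SD.

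**How much the missing formula leaves open.** At r = 0.8:

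- sqrt(2)*SEm with the standard error of measurement: sqrt(2*0.2) = 0.63 SD.
- Pooling the two occasions, with retest SD assumed 20% larger: sqrt((1 + 1.44)*0.2) = 0.70 SD.
- Prediction form, SD*sqrt(1-r^2): sqrt(0.36) = 0.60 SD.

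Largest over smallest is 0.699/0.600 = 1.16. The prediction form belongs with a numerator that uses a predicted retest score, not with the SAP's x2 - x1. The pooled form differs from the first only through the assumed larger retest SD.

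**The case for a change.** The best case for a change is that an analysis plan should not rely on the reader to correct its terms. The wrong name is on the page, it contradicts the method's stated purpose, and no formula settles the matter. The change metric is part of Specific Aim 3 and is meant to support a commercial tool. The correction would cost one term and one line, and fixing the term alone would still leave open which form of SEdiff is used.

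Part of this stands. The name is wrong, and the choice among forms of SEdiff is unwritten, with a spread of about 16% at r = 0.8 on the assumptions above. The large false-change rates do not stand as a consequence of the plan. To reach them, an analyst must ignore the verbal definition of SEdiff, import sqrt(2)*SEm from the reliable-change literature, and then insert a quantity that formula never uses. Anyone who knows the formula knows that SEm in it means measurement. The reliability coefficients in the same sentence would also have no purpose under the other reading.

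The open choice of form is partly deliberate. The SAP says a cut-off strategy will be identified from the data, and that the retest results will decide whether the calculations are adjusted.

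**Conclusion.** No change follows. Writing standard error of the mean for SEm is a clerical slip, and the missing SEdiff formula is a gap that analysts fill sensibly from the definition the SAP gives. The index as written divides by a quantity that is correctly defined and does not depend on sample size, so the RC rule is not shown to be wrong.

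The 46% to 86% figures and the attendance ratios of 0.58 and 0.71 rest on a formula absent from the SAP and on assumed r and n, so they do not measure a defect in this plan. What remains open is the choice among reasonable forms of SEdiff, a range of 0.60 to 0.70 SD at an assumed r = 0.8 and an assumed 20% larger retest SD. The 5% and 2.5% levels are exact per direction; a label would alter no cut-off and no result.

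This conclusion assumes that the analyst follows the SAP's verbal definition of SEdiff.

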3.2 Protocol 1 (Specific Aim 3)

The purpose of this protocol is to validate the CAMCI scoring algorithm on an independent sample of older individuals. Approximately 420 Adult male and female participants 60-95 years of age will be enrolled into this portion of the research study. Prior to enrollment, participants will be screened to determine eligibility for the study.

Baseline

After obtaining informed consent, participants will be asked to complete the MoCA, the CAMCI battery of tasks, a complete paper-pencil neuropsychological test battery, a survey requesting feedback from the participant concerning their experience with the CAMCI application, and a brief reading assessment. The paper-pencil tests will be used by three neuropsychologists (see Appendix A) to adjudicate the participants. The baseline test session will take approximately 2.5 hours to complete, and participants will be paid \$100 for completion of this portion of the study.

If an equivalent and valid neuropsychological task battery assessment (as determined by the project-certified examiner) is available at the time of enrollment in the study, the neuropsychological task battery will not be re-administered, and the protocol will be shortened to administer all remaining elements. In this case, total test session time is estimated to be approximately 60 minutes, and participants will be paid \$50 for completion of the shortened protocol.

Follow-Ups

Participants will be asked to return for two follow-up test sessions at set intervals in relation to their baseline test session (either 6 months and 12 months, or 12 months and 24 months). During the follow-up test sessions, participants will be asked to complete the MoCA, the CAMCI battery of tasks, and a complete paper-pencil neuropsychological test battery (the survey and reading assessment will not be repeated). Each follow-up test session will take approximately 2 hours to complete, and participants will be paid \$75 for each follow-up test session completed. Total compensation for each participant may be up to \$250 for completion of the baseline and 2 follow-up test sessions.

If a participant is unable to complete a test session, or if the experimenter must discontinue a test session before completion, the participant will be paid \$25.

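### CAMCI change must clear a measurement-error band, but one changed adjudicated class is enough for 'improved' or 'declined', so random reference error can enter the accuracy of the change metric

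*SAP*

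**What the plan says.** The Change Metric section of the SAP treats the two sides of the comparison differently.

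- **CAMCI side.** The difference between two scores is divided by SEdiff, which "will identify the variability in the distribution of the change scores that would be expected if there were no change between test and retest". Then "90% and 95% confidence intervals will be calculated to identify the amount of difference that would have to be observed in either direction", with the tail areas given as "at significance levels of 5% and 2.5%, respectively". The resulting index sorts people into gain, no change or loss.
- **Adjudication side.** In the sentence after that sorting, "the same individuals will be grouped based on change in clinical adjudication between those identified as impaired, intermediate, and non-impaired at each assessment", giving improved, no change or declined. No error band, minimum step, repeat adjudication, confirming visit or reliability estimate is stated for the adjudicated class.
- **Comparison.** "These groups will be analyzed based on the confidence intervals, accuracy, and reliable change index". The SAP adds that practice effect will be assessed.

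The SAP describes adjudication as a consensus classification and, under Agreement analysis, as the reference standard. Protocol 3.2 says that three neuropsychologists adjudicate from the paper-pencil tests. It also says: "Participants will be asked to return for two follow-up test sessions at set intervals in relation to their baseline test session". These are at 6 and 12 months or at 12 and 24 months, and each follow-up session includes both CAMCI and the battery.

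**The concern.** A consensus class based on one test session carries error. A stable person near the border between two classes can be placed on one side at baseline and on the other at retest. CAMCI has a tolerance for this kind of fluctuation; the class it is compared with has none. If CAMCI correctly shows no change in such a person, the comparison counts an error against CAMCI.

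The two measures are also taken in the same session, so a bad day can lower both and look like a detected decline. That would work in CAMCI's favour.

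The reported accuracy of the change metric would then mix CAMCI's error with an unmeasured amount of reference error. Each Protocol 1 participant has two planned follow-ups, so a class change at the first can be checked against the second, but the SAP does not use this.

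**Working it through.** **The plan's own figures.** The tail area of a two-sided band is (1 - confidence)/2: (1 - 0.90)/2 = 0.05 and (1 - 0.95)/2 = 0.025. These match the SAP. By design, then, 10% or 5% of stable people fall outside the CAMCI band, both directions combined. No corresponding rate is stated for adjudicated change.

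**Which retests can be confirmed.** The payment table in Protocol 4.11 plans 280 follow-ups at 6 months, 420 at 12 and 140 at 24, in total 280 + 420 + 140 = 840. Read with the two schedules in 3.2, 280 people are seen at 6 and 12 months and 140 at 12 and 24 (280 + 140 = 420). A later visit exists for all 280 six-month retests, for 140 of the 420 twelve-month retests and for none at 24 months: 420 of 840.

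**Illustrative model (assumptions, not from the documents).** A latent score plus independent error at three visits is cut at the 15th and 40th baseline percentiles (15/25/60% impaired, intermediate, non-impaired). Battery retest reliability is 0.85, 0.90 or 0.95. Of all participants, 15% decline by 0.8 SD of the baseline score by the first follow-up and stay there; nobody improves. CAMCI reliability is 0.80, the band is ±1.645 SEdiff, and the same-day error correlation is 0 or 0.3.

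| Battery reliability | 0.85 | 0.90 | 0.95 |
|---|---|---|---|
| Stable people changing class, single visit | 26% | 22% | 16% |
| Same, change required at both follow-ups | 13% | 11% | 8% |
| 'Declined' labels that are false, single visit | 60% | 55% | 46% |
| Same, change required at both follow-ups | 47% | 41% | 32% |

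Hand check at 0.90, where about 50% of true decliners are labelled declined: stable people contribute 0.85 × 0.22/2 = 0.094 and decliners 0.15 × 0.50 = 0.075, so the false share is 0.094/(0.094 + 0.075) = 0.55. Requiring confirmation lowers detection of true decliners from about 50% to 41%. If the 0.8 SD is scaled to the true score instead, the figures are 56% false (43% confirmed) and detection of 47% falling to 38%.

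**Effect on accuracy.** In SD units SEdiff = √(2 × (1 - 0.80)) = 0.632. A decline of 0.8 SD is 0.8/0.632 = 1.265 SEdiff, so the index shows loss with probability Φ(1.265 - 1.645) = 0.352. Three-way accuracy against true status is 0.85 × 0.90 + 0.15 × 0.352 = 0.82. Against single-visit status the simulation gives 0.65-0.74, and against confirmed status 0.75-0.79. At battery reliability 0.90, single-visit accuracy is 0.68 without and 0.70 with the same-day correlation; over the three reliabilities the shared error adds back only 1-2 points. Even a change metric with no error would score only 0.85 × 0.78 + 0.15 × 0.50 = 0.74 at reliability 0.90 against single-visit status, and about 0.82 against confirmed status.

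**Wider assumptions.** With reliability from 0.80 to 0.95, three other class mixes and 5-20% true decliners losing 1 SD, 14-35% of stable people change class and 31-86% of 'declined' labels are false. In a favourable case, where 5% of stable people change class and 80% of true changes are detected, the false share is 0.05(1 - q)/(0.05(1 - q) + 0.8q), where q is the proportion truly changing: 54%, 36% and 20% at q = 5%, 10% and 20%.

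**The case against.** The strongest reply is that the model is not the study's adjudication. The documents do not say that a single score is cut at fixed points; three neuropsychologists reach a consensus from several tests. Protocol 3.2 refers to Appendix A, which is not in the text reviewed, so a rule there on borderline cases or on use of earlier visits cannot be excluded. Every simulation above shares the same structure, so their agreement does not test it. This stands, and it limits the sizes to illustration. It does not remove the point: consensus reduces rater error but not day-to-day variation in the one battery that all three read, and assessing practice effect addresses a systematic shift, not random changes of class.

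It can also be said that the SAP uses the word 'reference' for the classification analysis and not for change. That is correct. Adjudicated change as the standard is an inference from the accuracy comparison, but no other comparator is named.

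Three stronger readings are tempting, and the documents do not support them.

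- A reader might infer that the change accuracy becomes uninterpretable because independent error lowers it and shared same-day error raises it. In every case of the illustrative model the net effect was downward, and the 0.3 correlation is an assumption.
- A reader might infer that all 'improved' labels are noise. That follows only from setting true improvement to zero.
- A reader might infer that confirmed status should become the basis for the conclusion. It is available for 420 of 840 planned retests and would mix two definitions at 12 months. It also compares both follow-ups with the same baseline class, so a baseline error can be 'confirmed' twice.

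**Conclusion.** The asymmetry is explicit in the SAP, and the stated safeguards do not cover it. Random error in the adjudicated class can enter the planned accuracy of the change metric, and the most likely direction is to understate it. The assumptions listed under the model give about 16-26% of stable people changing class at one retest, about 46-60% false 'declined' labels, and accuracy of 0.65-0.74 where 0.82 is true. None of these sizes can be fixed from the documents, which give no adjudication reliability, class mix or true change rate. The point justifies a pre-specified sensitivity analysis; it does not justify replacing the planned analysis.

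**What to change.** Keep single-visit status as the planned analysis and add to the last paragraph of Change Metric:

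1. A sensitivity analysis for first retests that have a later follow-up: all 6-month retests, and the 12-month retests on the 12/24-month schedule. 'Declined' or 'improved' requires the adjudicated class to be worse, or better, than baseline at both follow-ups. Every other pattern, including opposite directions, counts as 'no change'.
2. Reliable-change accuracy against single-visit and confirmed status side by side, separately by interval and schedule, so that the two definitions are not mixed at 12 months.
3. The share of first-follow-up class changes that revert, described as an indicator of reference instability. It also includes true recovery and practice, and it misses baseline error, so it is not a direct estimate of noise.
4. Status changes at a participant's last visit labelled as unconfirmed.

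The cost is SAP wording and an additional table from visits already planned. The drawbacks should be stated with the results: fewer status changes, true but reversible declines counted as no change, lower detection of true decliners, no confirmed status for people who miss the second follow-up, and false changes only about halved.
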